# Background

## Hypercapnic respiratory failure

Respiratory failure is a leading cause of morbidity and mortality, and one of the most frequently encountered problems at the emergency department.

Hypercapnic or hypercarbic respiratory failure, also dubbed respiratory failure type II, is characterized by failure of the respiratory system in one of its two gas exchange functions: carbon monoxide (CO2) elimination. It is thus usually defined via partial pressure of CO2 in the arterial blood gas (PaCO2), a value of higher than 50mmHg being a commonly used cut-off.

Hypercapnic respiratory failure is often associated with severe airway disorders, such as asthma and chronic obstructive pulmonary disease (COPD), but might also be found in other situations, where respiratory drive is restricted, such as intoxications, neuromuscular diseases or chest wall abnormalities.

Hypercapnic respiratory failure, i.e. respiratory failure type II, is often associated with hypoxic respiratory failure, i.e. respiratory failure type I, failure of oxygenation, however type I failure is also often observed without hypercapnia.

Respiratory failure, both type I and II, may be further classified into either acute or chronic. Distinction between both forms is often not easy, and, in addition to arterial blood gas analysis, might require additional tests to identify clinical markers such as polycythemia or cor pulmonale. For practical reasons, acute respiratory failure is often defined as a situation, in which respiratory failure develops too fast to allow for renal compensation and an increase in bicarbonate (HCO3) levels, and thus leading to acidosis (pH less than 7.3).

Therapy strategies for hypercapnic respiratory failure include non-invasive CPAP ventilation support, intubation and mechanical ventilation (both assisted and controlled forms), and, in very severe cases, extracorporeal methods, such as extracorporeal life support systems.

## Non-invasive CPAP Ventilation Support

Non-invasive CPAP ventilation support via either helmets, or different kinds of tight masks, is the current method of choice for the treatment of patients with acute respiratory failure in the intensive care setting. Eligible patients include those with an intact airway, airway-protective reflexes, who are alert enough to follow commands, whereas patients who lack those criteria require immediate intubation.

Non-invasive CPAP ventilation support improves both oxygenation (by providing an inspired fraction of oxygen (FiO) of 100%, which is not possible via a simple venturi-mask, and the possibility of positive end-expiratory pressure (PEEP), preventing collapsing of the alveoli), and decarboxylation (by increasing tidal volume). It has been shown to decrease both need for intubation and in-hospital mortality.

Non-invasive CPAP ventilation support however requires a high grade of skill from providers, and intensive communication with the patient to explain to him the usefulness of a tight-sitting device in his face in a situation of perceived massive dyspnea. Although severe adverse effects of non-invasive CPAP ventilation support are very rare, pain and pressure marks may occur. Despite all efforts of care providers, there is a relevant fraction of patients who do not tolerate ventilation support via a tight mask at all. Brochard et al. report 15% of patients not tolerating the therapy, with an additional 25% of patients presenting with contraindications. These might include general contraindications against non-invasive techniques, such as aforementioned lack of airway-protective reflexes, but also such specific for tight masks, such as anatomical abnormalities of the face.

## High-flow Nasal Oxygen

High-flow nasal oxygen (HFNO2) therapy is usually applied via a wide-bore nasal cannula. It provides up to 60L/min of a heated and humidified gas mixtures (at an adjustable mix medical of oxygen and room air). This therapy is much less invasive for the patient, and thus often better tolerated.

HFNO2 has been increasingly used in the last years for hypoxic respiratory failure (i.e. type I failure), and numerous studies have shown its efficiency in this indication both at the intensive care unit and at the emergency

department. A recent systematic review and meta-analysis has concluded in improved patient comfort and reduced dyspnea scores.

Despite this good evidence for HFNO2 in hypoxic respiratory failure, it has only reluctantly been used for hypercapnic respiratory failure. This might in a large part be explained by the fact that patients with chronic hypercapnia are known to diminish their respiratory drive when exposed to hyperoxia. However, evidence has begun to change on this indication in recent time. HFNO2 has been shown to generate PEEP, despite not being a closed system^18, and to improve CO2 clearance by flushing anatomical dead space. It might also help to reduce inspiratory resistance and facilitate secretion clearance from humidified gas. A study on COPD patients showed an increase in breathing pressure amplitude and mean pressure, as well as tidal volume, with a trend towards reduction of pCO2.

Based on these findings, the use of HFNO2 has increased in clinical practice, and a number of case reports and -series indicate successful use. Fraser et al. successfully investigated the use of HFNO2 in patients with chronic COPD, and Jeong et al. retrospectively analyzed changes in arterial blood gases during use of HFNO2 in the ED for both hypercapnic and non-hypercapnic patients, and found a significant reduction of pCO2.

There is, however, to date no randomized controlled trial investigating the effect of HFNO2 in acute hypercapnic respiratory failure.

### Objectives

To assess the efficacy and safety of HFNO2 versus non-invasive CPAP ventilation support in acute hypercapnic respiratory failure.

# Study

## Setting

The study will be performed as a randomized controlled on-inferiority trial.

The study site is the Department of Emergency Medicine (ED) of the Vienna General Hospital, a leading academic research center for emergency medicine at a large, tertiary care hospital.

Around 90,000 patients are being treated at the department each year, approximately 150-200 of them suffering from hypercapnic respiratory failure, and requiring non-invasive ventilation support.

The department features its own ICU and intermediate-care unit, with 7 positions each, for a total of 14 positions capable of providing CPAP therapy. The Airvo II HFNO2-device is also at regular use at the department.

## Sponsoring

Sponsor of this study will be the Department of Emergency Medicine at the Medical University Vienna. There is no industry sponsoring or industrial financial support, but we will apply for financial support from research grants.

## Registration and Regulation

This project is considered as a study investigating differences of two standard medical methods. This study will be submitted for review and approval to the ethical committee of the Medical University Vienna and the Vienna General Hospital. The office of the medical Director will be announced, and the study will be registered at <http://www.controlled-trials.com/>.

# Population

## Inclusion criteria

- Adult patients (e.g. at least 18 years old) treated at the Emergency Department
- Acute hypercapnic respiratory failure defined as a  $pCO_2 > 50 \text{ mmHg}$  and a  $pH < 7.3$  on admission

## Exclusion criteria

- Patients being comatose on admission, with no intact airway, lack of airway-protective reflexes, or those who are not alert enough to follow commands
- Patients intubated by Emergency Medical Service
- Patients requiring intubation on admission
- Pregnant women

# Outcome

## Primary outcome

- Reduction of  $pCO_2$  per hour

## Secondary outcomes

### Clinical and safety Parameters

- Frequency of therapy failure (switch to other therapy; intubation)
- Patient's perception of the therapy (10-point Likert-Scale from very uncomfortable to very comfortable)
- Adverse events

### Efficacy Parameters:

- Time until  $pCO_2$  reaches 50mmHg or less

### Economic Parameters:

- Length of Stay at the Emergency Department

- Frequency of admission to ICU
- Frequency of admission to regular ward
- Length of Stay at the ICU
- Length of Stay at the Hospital
- Hospital readmission within 1 month

## Methods

### Randomisation

A random sequence will be generated by a person not involved in the enrolment of patients using standard software. Randomisation will be performed in variable blocks of 4 to 6, to yield an unpredictable allocation yet warranting balanced group sizes.

Sequentially numbered sealed opaque envelopes (SNOSE), containing allocation either to the intervention or the control group, will be pre-produced. The envelopes will be opened after consent immediately before the start of the intervention to allow for allocation concealment and reduce the risk of immediate post-random exclusion.

### Intervention

Control consists of HFNO2 using the Airvo II, Fisher & Paykel, New Zealand. A gas flow 60L/min and and a FiO2 as clinically feasible will be used. Therapy will be continued until a COHb-level of 50mmHg or less is reached, or therapy has to be aborted because of lack of tolerance by the patient or indication for intubation.

### Measurement

Baseline characteristics and demographic variables will include age, sex, smoking status, prior diseases, especially any history of COPD or Asthma, and duration of treatment of those, medication, body size, pre-hospital treatment. pCO2 levels will be measured using blood gas analysis at 0 – 15 – 30 – 45 – 60 – 90 – 120 (and every 30 minutes thereafter) minutes after the beginning of the therapy, and at the end of the therapy.

Patient's perception of the therapy will be assessed after the end of the therapy using a 10-point Likert-Scale from very uncomfortable to very comfortable.

In case of abortion of assigned therapy, we will follow a carry-on-latest principle, by calculating pCO2 reduction per hour by dividing actual reduction of pCO2 during assigned therapy by total treatment time (including follow-on therapy after abortion), to achieve a maximally conservative interpretation of therapy effect.

## Statistics

### Sample size

Sample size considerations are based on the primary outcome  $pCO_2$  reduction per hour. Based on the published literature, we assume that the outcome in the control group is  $4\pm3\text{mmHg/hour}^8$ . Based on a clinically assumed non-inferiority of 2mmHg we would need 28 experimental subjects and 28 control subjects to be able to reject the null hypothesis, that the lower limit of a two-sided 90% confidence interval of the true difference between two groups is above the non-inferiority limit, at a power of 80%. Formally we will have to enrol 56 patients. To allow for potential loss to follow up, missing data, measurement issues, or other design factors we will increase actual sample size to 62.

In terms of feasibility, we expect approximately 150 to 200 eligible patients within one year, resulting in an expected study-duration of approximately 6 months.

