### Data Analysis

Baseline data and demographics will be tabulated for the intervention- and control-group to assess success of randomisation. Reduction of  $pCO_2$  per hour will be calculated by dividing delta  $pCO_2$  at start of therapy to end of therapy by duration of therapy in hours. In case of abortion of assigned therapy, we will follow a carry-on-latest principle, by calculating  $pCO_2$  reduction per hour by dividing actual reduction of  $pCO_2$  during assigned therapy by total treatment time. Reduction of  $pCO_2$  per hour will be compared between individuals in the intervention and individuals in the control group. Primary analysis will follow the intention-to-treat principle. The unit of analysis will be single persons. We will calculate effects as differences with 95% confidence intervals. For hypothesis tests we will use the t-test or Mann-Whitney-U-test, as appropriate. In case of relevant clustering we will use regression-based approaches.

Categorical secondary outcomes will be analysed by calculating relative risks with exact standard error based 95% confidence intervals, and the Fisher's exact test will be used for comparison. Continuous secondary outcomes will be analyzed like the primary outcome. Length of stay data are expectedly lognormally distributed, therefore we plan to use log-transformed values for further calculations.

For data analysis we will use Stata 11. A two-sided p-value less 0.05 is generally considered statistically significant.

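### The trial is sized for a 90% confidence limit against a 2 mmHg margin, but Data Analysis gives 95% intervals and ordinary two-sided tests and never uses the margin

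*Protocol*

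**What the plan says.** Under Setting, the protocol states: "The study will be performed as a randomized controlled on-inferiority trial" (an evident misprint for non-inferiority).

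Sample size works from pCO2 reduction per hour, taken as 4±3 mmHg/hour in the control group. It continues: "Based on a clinically assumed non-inferiority of 2mmHg we would need 28 experimental subjects and 28 control subjects". The stated power is 80%, and the hypothesis to be rejected is the "null hypothesis, that the lower limit of a two-sided 90% confidence interval of the true difference between two groups is above the non-inferiority limit". The total of 56 is raised to 62 to allow for losses.

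Data Analysis says of the primary outcome: "We will calculate effects as differences with 95% confidence intervals. For hypothesis tests we will use the t-test or Mann-Whitney-U-test, as appropriate". It adds: "A two-sided p-value less 0.05 is generally considered statistically significant". It mentions neither the margin nor a 90% interval, and it makes no exception for the primary comparison. Continuous secondary outcomes are to be handled in the same way as the primary one.

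**The concern.** The two sections treat one primary outcome at two confidence levels, and only one of them refers to a margin. A result can meet the non-inferiority criterion with a 90% interval and miss it with a 95% interval. If the choice between them is left until results are known, the primary conclusion is open to selection. The stated 80% power also belongs to the 90% rule only.

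The tests named in Data Analysis carry no shift by the margin, so they test for no difference. A non-significant result from such a test does not show non-inferiority, and nothing in the section guards against reading it that way. A Mann-Whitney p-value also provides no interval for a mean difference to set against the margin.

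Separately, the null is written the wrong way round and in terms of a confidence limit rather than a parameter. This is a wording error. The intended rule can be recovered from the sentence, and the sample size and power are unaffected. It does mean that no section states the decision rule cleanly.

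**Working it through.** **Inputs.** From Sample size: SD 3 mmHg/hour (given for control only), margin 2, power 80%, two-sided 90% interval (one-sided 5%), 28 per arm, 62 enrolled (31 per arm). From Data Analysis: two-sided 95% interval (one-sided 2.5%).

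**Assumptions.** SD 3 in both arms; true difference 0 (not stated); margin read as 2 mmHg per hour, because the outcome is a rate although the protocol prints only mmHg. Differences are HFNO2 minus CPAP in pCO2 reduction per hour.

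**1. The protocol's own figure.** n per arm = 2 × (z₁₋α + z₀.₈₀)² × SD² / margin².
- One-sided 5%: 2 × (1.645 + 0.842)² × 9 / 4 = 27.8, so 28. This matches the protocol (29 by noncentral t).
- One-sided 2.5%: 2 × (1.960 + 0.842)² × 9 / 4 = 35.3, so 36 (37 by noncentral t). This does not give 28.

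The design therefore rests on the 90% rule.

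**2. Power of the planned sample.** SE = 3 × √(2/n), which is 0.802 at 28 per arm and 0.762 at 31. Normal approximation: power = Φ(2/SE − z₁₋α). Ranges run from noncentral t to normal.

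| Evaluable per arm | 90% interval decides | 95% interval decides |
|---|---|---|
| 28 | 0.793-0.802 | 0.688-0.703 |
| 31 | 0.829-0.836 | 0.733-0.747 |

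**3. Where the rules part.** With an observed SD of 3, the smallest observed difference that passes is −2 plus the interval's half-width.
- 28 per arm: half-widths 1.342 (90%) and 1.607 (95%), so cut-offs −0.658 and −0.393.
- 31 per arm: half-widths 1.273 and 1.524, so cut-offs −0.727 and −0.476.

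Between each pair of cut-offs, the same data are non-inferior under one rule and not under the other. At a true difference of 0, the probability of disagreement is 0.793 − 0.688 = 0.105 at 28 per arm and 0.829 − 0.733 = 0.096 at 31.

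**4. The unshifted test.** If HFNO2 were truly worse by the full 2 mmHg/h, a two-sided t-test at 0.05 would be non-significant with probability 0.312 at 28 per arm and 0.267 at 31 (noncentral t).

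**5. A shifted rank test.** A Mann-Whitney test shifted by the margin was simulated (20,000 runs, normal data, SD 3, 28 per arm, one-sided 5%). It rejects in 4.9% of runs at a true difference of −2 and in 77% at 0. The rank test is usable once shifted.

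**6. Size needed if 95% decides.** At the protocol's own 62/56 allowance: 72 × 62/56 = 79.7, so 80 enrolled; or 74 × 62/56 = 81.9, so 82.

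**The case against.** Sample size is the only section that states a non-inferiority criterion, and Data Analysis does not state a rival one. A trial can report 95% intervals while deciding on a 90% interval, and the word generally, attached to the 0.05 threshold, leaves room for an exception. On that reading, the 95% non-inferiority rule is an inference, the missing margin is detail that an analysis plan could supply, and the sample size is correct for its own rule. If the 95% interval did decide, the error would be on the conservative side.

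Much of this stands. The 28 per arm is right for the 90% rule, so the trial is not undersized under that rule. The 95% reading is stricter and does not raise the false-positive rate. The reversed null is a secondary point.

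It does not remove the problem. Data Analysis applies its interval and tests to the primary outcome, does not call them descriptive, and names no exception. A separate analysis plan, which was not available here, could choose between the levels, but the protocol would still give two. The unshifted tests would still not answer a non-inferiority question.

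**Conclusion.** The concern holds and must be fixed, because it affects the trial's single confirmatory conclusion. The sample size is valid only for a 90% interval set against the margin, whereas Data Analysis prescribes a different level and tests that ignore the margin.

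If the 95% interval decides, power is 69-70% with 56 evaluable patients and 73-75% only if all 62 are evaluable, against the 80% stated. The two rules give opposite conclusions in about 10% of trials when the treatments are truly equal. Reading a non-significant unshifted t-test as non-inferiority would be wrong 27-31% of the time at a true deficit equal to the margin. All of these figures depend on the common SD of 3 and the per-hour margin; the power and disagreement figures also depend on a true difference of 0. The contradiction between the sections does not depend on any of these assumptions.

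**What to change.** State the null as mean(HFNO2) minus mean(CPAP) ≤ −2 mmHg/h in pCO2 reduction per hour, and print the margin with its per-hour unit. In both sections, say that non-inferiority is concluded if the lower confidence limit for the mean difference lies above −2 mmHg/h. Then fix one confidence level by one of these routes:

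- **(a)** Carry the 90% interval (one-sided 5%) into Data Analysis and label the 95% intervals and two-sided difference tests descriptive or secondary. This matches the existing sample size and costs wording only.
- **(b)** Keep 95% and restate power as about 69-70% (56 evaluable) or 73-75% (62 evaluable). This also costs wording only, but the stated power is less favourable.
- **(c)** Keep 95% and resize to 36-37 evaluable per arm, about 80-82 enrolled. That is 18-20 more patients; at the planned pace of 62 in about 6 months, recruitment takes 6 × 80/62 = 7.7 to 6 × 82/62 = 7.9 months. This route is optional and is needed only if the sponsor wants both 95% and 80% power.

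Under any route, state that a non-significant unshifted t-test or Mann-Whitney test is not evidence of non-inferiority. Any rank-based sensitivity analysis should be shifted by the margin or use a Hodges-Lehmann interval.

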### Data Analysis

Baseline data and demographics will be tabulated for the intervention- and control-group to assess success of randomisation. Reduction of  $pCO_2$  per hour will be calculated by dividing delta  $pCO_2$  at start of therapy to end of therapy by duration of therapy in hours. In case of abortion of assigned therapy, we will follow a carry-on-latest principle, by calculating  $pCO_2$  reduction per hour by dividing actual reduction of  $pCO_2$  during assigned therapy by total treatment time. Reduction of  $pCO_2$  per hour will be compared between individuals in the intervention and individuals in the control group. Primary analysis will follow the intention-to-treat principle. The unit of analysis will be single persons. We will calculate effects as differences with 95% confidence intervals. For hypothesis tests we will use the t-test or Mann-Whitney-U-test, as appropriate. In case of relevant clustering we will use regression-based approaches.

Categorical secondary outcomes will be analysed by calculating relative risks with exact standard error based 95% confidence intervals, and the Fisher's exact test will be used for comparison. Continuous secondary outcomes will be analyzed like the primary outcome. Length of stay data are expectedly lognormally distributed, therefore we plan to use log-transformed values for further calculations.

For data analysis we will use Stata 11. A two-sided p-value less 0.05 is generally considered statistically significant.

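### The primary comparison is unadjusted although time-0 pCO2 is always at hand; adjusting for it is a cheap precision improvement whose gain is small and possibly nil

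*Protocol*

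**What the plan says.** The Data Analysis section defines the primary outcome as the change in pCO2 "at start of therapy to end of therapy by duration of therapy in hours". It names the test: "For hypothesis tests we will use the t-test or Mann-Whitney-U-test, as appropriate". No covariate is named for it. Regression appears only for another purpose: "In case of relevant clustering we will use regression-based approaches". Baseline variables have one stated use: "Baseline data and demographics will be tabulated for the intervention- and control-group to assess success of randomisation".

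The Measurement section schedules the covariate in question: pCO2 "levels will be measured using blood gas analysis at 0" minutes and at set times afterwards.

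The Sample size section plans on an SD of 3 around a control mean of 4 mmHg/hour and on a margin introduced as "Based on a clinically assumed non-inferiority of 2mmHg". It judges the lower limit of a two-sided 90% interval and arrives at 28 per arm, raised to 62 in total.

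**The concern.** Time-0 pCO2 is the natural covariate for this outcome. It is the first term of the numerator, so any patient whose outcome can be computed has it. It may also influence the divisor, because treatment ends in response to a measured level: "Therapy will be continued until a COHb-level of 50mmHg or less is reached". For this point I read the printed COHb as pCO2, matching the 50 mmHg threshold under Efficacy Parameters. The label needs reconciling, but none of the power figures depends on it.

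With 62 patients the arms can differ by chance in time-0 pCO2. If that value is correlated with the hourly fall, the imbalance adds avoidable variation to a difference judged against 2 mmHg/h. Prespecifying the covariate also removes the temptation to adjust after the baseline table has been seen.

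**Working it through.** **Inputs from the protocol.** SD 3 mmHg/h, margin 2, 80% power, 90% two-sided interval (one-sided 0.05), 28 per arm, 62 in total (Sample size); 95% interval (Data Analysis). The true difference is taken as 0. **Assumed:** r, which the protocol does not give.

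**1. The plan's own figure.** n per arm = 2 × 3² × (1.645 + 0.842)² / 2² = 27.8, so 28. The stated number is reproduced.

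**2. Unadjusted, 31 per arm.** SE = 3 × √(2/31) = 0.762. Noncentrality = 2 / 0.762 = 2.62 on 60 df. Power is 82.9% and the 90% half-width is 1.671 × 0.762 = 1.27 mmHg/h.

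**3. Adjusted, 31 per arm.** Residual SD = 3 × √(1 − r²) on 59 df. The SE is inflated by √(1 + t²/60), with t distributed as t on 60 df, to allow for chance baseline imbalance; power is averaged over t. The expected variance relative to unadjusted is (1 − r²) × (1 + 1/58). The patient equivalent is 62 / ratio − 62.

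| Assumed \|r\| | Variance ratio | SE change | Patients on 62 | Power, 90% CI | Power, 95% CI |
|---|---|---|---|---|---|
| unadjusted | 1 | – | – | 82.9% | 73.3% |
| 0 | 1.017 | +0.9% | about −1 | 82.3% | 72.6% |
| 0.17 | 0.988 | −0.6% | about +1 | 83.3% | 73.8% |
| 0.3 | 0.926 | −3.8% | about +5 | 85.4% | 76.5% |

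At 28 per arm with a 90% interval, power is 79.3% unadjusted against 78.7%, 79.7% and 81.9%.

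**4. Break-even.** The ratio equals 1 when r² = 1/59, so |r| = 0.13. Below that, adjustment costs slightly more than it returns.

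**5. Where r may lie.** This can only be explored by simulation on assumed inputs. The protocol's blood-gas schedule and stopping at 50 mmHg were combined with three baseline means (60, 68, 75), three noise levels, two spreads of true rate and three shapes of decline, giving 54 scenarios. One such grid gave a median |r| of 0.17. Two further runs of similar grids put about 21 and 30 of the 54 below 0.13, that is 39% and 56%. The sign of r also depended on the assumed shape of decline.

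**6. Chance imbalance.** A baseline imbalance of 1.96 SE, a 5% event counting both directions, shifts the unadjusted difference by r × 0.762 × 1.96. That is 0.25 mmHg/h at r = 0.17 (13% of the margin) and 0.45 at r = 0.3 (22%). The unadjusted interval already allows for this variation; adjustment removes it.

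**7. Expected difference.** In eight simulated settings under linear decline (true difference 0 or −2), the adjusted and unadjusted means agreed within 0.006 mmHg/h. Adjustment changes precision and leaves the target as it is.

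**The case against.** The strongest case against raising this is that covariate choice is commonly left to a SAP, which is not at hand, and that nothing in the protocol is wrong: the test is valid and matches the sample-size calculation. The second half stands fully. The first does not settle the matter, because the protocol names its method, gives regression another use and gives baseline data a descriptive one. The proposal replaces a stated method with a concrete one.

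It is also fair to say that the gain is often negligible. At |r| = 0.17 it is 0.4 power points, and in some 40% or more of the simulated scenarios precision falls slightly. Adjustment is therefore cheap, not free. Larger correlations should not be relied on. The grid in step 5 left out aborted courses, for which the protocol divides the fall on assigned therapy by total treatment time. Adding 15% aborted, the intolerance rate cited in the Background, lowered the largest positive correlation in both re-runs.

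The choice between 90% and 95% intervals matters more (82.9% against 73.3% unadjusted), but it is a separate issue that adjustment does not resolve. Finally, a linear model displaces the Mann-Whitney option, so the proposal must say what becomes of it.

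A reader might infer that the unadjusted analysis is biased towards non-inferiority. Randomisation rules that out, and step 7 agrees.

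**Conclusion.** The point holds as a minor, optional improvement. The protocol fixes an unadjusted primary comparison and leaves unused a baseline value that it collects for every patient. At 31 per arm and a 90% interval, adjustment changes power from 82.9% to between 82.3% and 85.4% for |r| from 0 to 0.3: a loss of about one patient's worth of precision at worst, and a gain of about five at |r| = 0.3. These figures rest on the planned SD of 3, a true difference of 0 and an r that the protocol does not supply.

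A reader might also infer that the trial is underpowered for want of adjustment. The documents do not support that: the SD of 3 is stated for the outcome itself, and 28 per arm is correct for an unadjusted comparison under the 90% interval.

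**What to change.** State in Data Analysis that the primary between-arm difference (HFNO2 minus CPAP) and its confidence interval come from a linear regression of hourly pCO2 reduction on treatment and time-0 pCO2, and that the lower limit is compared with −2 mmHg/h. Keep the unadjusted comparison, including Mann-Whitney for marked skewness, as a sensitivity analysis. Outcome, margin and sample size stay as they are.

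The cost is a sentence or two of wording and one degree of freedom, with no new measurements or patients. If |r| turns out below about 0.13, the standard error is up to 0.9% larger.

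### The log-scale analysis cannot include patients with no ICU stay, and, separately, readmission and length of stay take no account of death; both defects affect secondary economic outcomes only

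*Protocol*

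**What the plan says.** The protocol's list of economic parameters has six items. Three are lengths of stay (emergency department, ICU, hospital), two are admission frequencies, and one is readmission. Two entries matter together: "Length of Stay at the ICU" is not limited to admitted patients, and "Frequency of admission to ICU" is a separate outcome, so admission is not expected in everyone. The last item is "Hospital readmission within 1 month", with no condition on discharge alive.

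The Data Analysis section then sets the methods:

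- Lengths of stay: "Length of stay data are expectedly lognormally distributed, therefore we plan to use log-transformed values for further calculations".
- Other continuous secondary outcomes: "Continuous secondary outcomes will be analyzed like the primary outcome", that is, a difference with a 95% confidence interval and a t-test or Mann-Whitney test.
- Binary outcomes, including readmission: "Categorical secondary outcomes will be analysed by calculating relative risks with exact standard error based 95% confidence intervals", with Fisher's exact test.
- Analysis set: "Primary analysis will follow the intention-to-treat principle". No set is named for the secondary outcomes.

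No section says how a zero ICU stay or a death enters these analyses. Mortality is not among the primary or secondary outcomes. Adverse events are listed under the clinical and safety parameters. The Background credits the control therapy with having been shown to "decrease both need for intubation and in-hospital mortality".

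**The concern.** There are two defects, and they work through different routes.

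The first concerns ICU stay. A single distributional statement covers all three stay variables, but a variable with zeros cannot be lognormal. If the log is taken as planned, patients never admitted have no value. What remains compares people selected by an event after randomisation, and that event is itself an outcome that treatment may change. The arm that uses the ICU more, with extra short stays, could then appear to have the shorter ICU stay.

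The second concerns death. A patient who dies in hospital cannot be readmitted and so adds a non-event to that arm. A patient who dies early adds a short stay. With no mortality outcome beside them, these results can be misread if deaths differ between arms. That matters in a non-inferiority trial against a therapy that the protocol itself links to lower mortality.

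**Working it through.** The protocol states no figure for these outcomes that could be reproduced. It gives the planned total of 62 (31 per arm) but no mortality, ICU admission or readmission rate and no stay distribution. Every such rate below is an assumption, used to show direction and range.

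**ICU stay: patients left.** The log is defined only for admitted patients, so the number analysed is 62 × admission rate:

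- 20%: 62 × 0.20 = 12.4
- 40%: 62 × 0.40 = 24.8
- 60%: 62 × 0.60 = 37.2

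**ICU stay: a possible reversal.** Assume arm A admits 30%, with lognormal stays of median 6 days and log-SD 0.7. Arm B admits the same 30% plus a further 20% with median 2 days and the same log-SD.

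- Among admitted patients, 20/50 = 0.4 of arm B are the short stays. The geometric mean ratio B/A is (2/6)^0.4 = 0.64, which favours B.
- The mean of a lognormal is median × exp(0.7²/2) = median × 1.278. Mean ICU days per randomised patient are 0.30 × 6 × 1.278 = 2.3 in A, and 2.3 + 0.20 × 2 × 1.278 = 2.8 in B, which is against B.

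The log-scale result points to the arm that used more ICU days. Deaths play no part in this example.

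**Hospital stay and death.** Suppose a fraction p more patients die in one arm, with median stay m_d instead of the survivors' m_s. The geometric mean ratio is then (m_d/m_s)^p. With m_s assumed to be 7 days:

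| Extra deaths (p) | Deaths at 2 days | 5 days | 10 days |
|---|---|---|---|
| 0.05 | 0.94 | 0.98 | 1.02 |
| 0.10 | 0.88 | 0.97 | 1.04 |
| 0.15 | 0.83 | 0.95 | 1.05 |

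For example, exp(0.10 × ln(2/7)) = exp(−0.125) = 0.88. The ratio is below 1 only if deaths come earlier than survivors typically leave.

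For scale, assume a log-SD of 0.8. With 31 per arm the standard error of the log ratio is 0.8 × √(2/31) = 0.203. A 95% interval then runs from about 0.67 to 1.50 times the estimate, so a 12% shift lies well inside it.

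**Readmission and death.** If a fraction d die before discharge and the readmission risk r among those discharged alive is the same in both arms, the risk per randomised patient is r(1 − d). The relative risk is (1 − d_B)/(1 − d_A).

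- Mortality 10% v 20%: 0.80/0.90 = 0.89.
- Mortality 10% v 30%: 0.70/0.90 = 0.78.

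Both favour the arm with more deaths. At r = 20% and mortality 10% v 20%, readmission is 18% v 16%, a difference of 0.02 × 31 = 0.6 events per arm. Counting death or readmission gives 10% + 18% = 28% v 20% + 16% = 36%, and the ordering turns round.

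**The case against.** The best defence is that only the protocol is at hand, and rules for zeros and deaths in secondary outcomes often sit in an SAP. The protocol does not say that patients without an ICU stay are dropped; that follows from the transformation. This stands as far as missing detail goes. It does not rescue the method that is stated, which cannot be applied to the ICU variable without being changed. Nor can an SAP supply 1-month vital status if it is not collected.

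Second, the outcomes are labelled economic, and a stay that ends in death does use fewer bed-days. That is fair, and it is a reason to keep plain bed-days as resource use and add a death-aware display beside them. Third, admission frequency plus stay among those admitted is a recognisable two-part description. That also is fair, but the protocol does not present it so, and the second part is not a randomised comparison.

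A reader might infer more than the document supports:

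- *That dropping zero ICU stays makes an arm with more deaths look better.* It does not; that selection runs through ICU admission.
- *That deaths would go unseen.* They may be reported as adverse events. What is missing is a named mortality outcome and a link to the stay and readmission analyses.
- *That early death shortens stay by some definite amount, such as 12%.* That figure needs an assumed 2-day stay in those who die. At 5 days it is 3%, and at 10 days the sign reverses.
- *That listing mortality would let the trial show or exclude a survival effect.* With 62 patients, sized on pCO2 reduction, it would not.

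**Conclusion.** Both defects hold, for secondary economic outcomes only. The primary outcome, the sample size and the non-inferiority conclusion do not depend on them, so this should be corrected but does not threaten the main result.

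The ICU defect is certain in kind, because a log-scale analysis cannot include zero stays and the protocol's own outcome list implies that zeros will occur. How many patients are lost, and whether the comparison is distorted, depends on admission rates that the protocol does not give. For readmission, if risk among those discharged alive is equal, more deaths always lower the apparent rate. For length of stay, neither the size nor the sign can be fixed from the document: the 0.88, 0.97 and 1.04 for 10 extra percentage points of deaths all rest on the assumed 7-day median in survivors and the assumed timing of death. If mortality is equal and deaths fall at similar times in both arms, neither death-related distortion arises.

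**What to change.** **ICU stay.** Compare ICU days in all randomised patients, with zeros kept, by a rank-based test (Mann-Whitney is already in the plan), and report mean days per arm. Alternatively, use ICU-free days over a stated horizon, such as 30 days, with deaths set to 0. Present any log-scale result among admitted patients as descriptive only.

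**Readmission.** Analyse death or readmission within 1 month as one binary outcome with the planned relative risk and Fisher's exact test.

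**Mortality.** Tabulate all-cause death in hospital and at 1 month by arm, as description and not as a test.

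**Hospital stay.** Show it also as time to discharge alive, with death as a competing event.

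**Cost.** The change is analysis wording plus one data item: vital status, recorded when 1-month readmission is ascertained. The Measurement section describes no 1-month contact, so the protocol should say how both are obtained. The results are slightly less simple to read than mean days. Treatment and sample size do not change.
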